criteria: a) use of illegal drugs except cannabis (as determined by the Drug Use Disorders Identification Test-Extended [DUDIT-E], [3]); b) alcohol abuse (i.e., AUDIT \geq 20); consumption of medical drugs with psychoactive effects (e.g., sedatives or anxiolytics) during the two weeks before the experiment; c) personal history of psychopathological disorders (according to DSM-V criteria); d) history of traumatic brain injury or neurological disorder; e) family history of alcoholism or diagnosis of other substance abuse; f) occurrence of one or more episodes of loss of consciousness for more than 20 minutes; g) non-corrected sensory deficits; h) Global Severity Index (GSI) $>$ 90 (Symptom Checklist-90-Revised questionnaire [SCL-90-R], [4]) or a score above 90 in at least two of the symptomatic dimensions.

Quality assurance and randomization

The protocol will be implemented by three skilled researchers with expertise in behavioral and EEG assessments and tDCS interventions. Researchers will not be aware of the results of the pre-training EEG assessment and will be blind to the randomization procedure that will follow. The randomization of the BD groups will be performed by an independent researcher using Microsoft Excel. BDs will receive one of the following interventions: 1) Combined training (verum CT and tDCS applied over the right dorsolateral prefrontal cortex); 2) Cognitive training (active CT and sham tDCS); or 3) Control (sham CT and sham tDCS). Based on this experimental procedure, it is expected that researchers will be able to answer the following research questions:

1. How does BD affect alcohol-related MI in young adults? Namely, are the behavioral and electrophysiological MI mechanisms - specifically those related to the suppression of alcohol-related memories - altered in BDs when compared to non/low-drinkers?

2. What is the effect of a MI training on behavioral TNTA task performance?

Specifically, will the BDs show a reduced recollection of no-think images - mainly for alcoholic no-think images – after training?

3. Are the electrophysiological correlates underlying MI mechanisms and alcohol cue reactivity changed by MI training?

4. Will the MI training reduce alcohol consumption and craving levels at 10-day and 3-month follow-ups?

Experimental tasks

Alcohol Cue Reactivity (ACR) task

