During the Learning phase, participants are asked to memorize 36 image-pairs (i.e., a neutral image paired with an image including alcoholic or non-alcoholic drinks) divided into three blocks of 12 pairs. Each block starts with the presentation of the 12 image-pairs at the center of the screen, each for 4000 ms, in a randomized order, and with an inter-stimuli interval (ISI) ranging from 1000 to 2000 ms. When the presentation of the 12 pairs finished, each of the neutral images are presented for 2000 ms, and the participants must try to remember the image that was associated with the neutral object through three questions: Q1. “Which beverage was associated with this picture?”; Q2. “How was the picture oriented?”; Q3. “How many people were there in the picture?”. In each block, the 12 pairs and the questions are repeated three times. At the end of each block, feedback with the total number of correct responses will be provided. Correct recall will only be considered when participants provide the right answer to the 3 questions.

Thus, the combination of the potential answers to the 3 questions ($6 \times 2 \times 3 = 36$) ensured that each target image displayed a unique combination.

TNT Phase

In this phase, there are two possible actions: to Think or to No-Think on the alcoholic/non-alcoholic image paired with the neutral object previously. Specifically, in the Think condition – determined by a green frame that circumvents the neutral image -, participants will be asked to focus on the neutral image and think in the alcoholic/non-alcoholic image that was associated with it (i.e., the one that was paired with this specific neutral image). In the No-Think condition - determined by a red frame that circumvents the neutral image -, participants are instructed to focus on the image and to not let the previously associated alcoholic/non-alcoholic picture enter their consciousness. All the images will be presented for 3000 ms and randomly repeated 10 times and presented for four seconds at the center of the screen with an offset-onset ISI ranging from 1100-1300 ms. From the initial set of 36 neutral images shown in the learning phase only 24 will be depicted during the TNT phase, 12 in each condition (i.e., Think vs No Think). The remaining 12 neutral images not depicted in this phase will serve as a baseline condition for the following Memory-Test phase of the task.

Memory -Test Phase

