## Abstract

**Background:** Binge Drinking (BD), a pattern of alcohol misuse widely prevalent among youngsters, has been associated with altered inhibitory control and augmented reactivity to alcohol-related information. Memory inhibition (MI), the ability to voluntarily suppress unwanted thoughts or memories, has shown to lead to forgetting of memories in several psychiatric conditions. However, despite its potential clinical implications, no study to date has explored the MI abilities in populations with substance misuse, such as binge drinkers (BDs).

**Method:** This study protocol aims firstly to examine the behavioral and electroencephalographic (EEG) correlates of MI among college BDs. For this purpose, 45 BDs and 45 age-matched non/low-drinkers will be assessed by EEG while performing the Think/No-Think Alcohol task, a paradigm that evaluates alcohol-related MI. Additionally, this work aims to evaluate an alcohol-specific MI training protocol using cognitive and transcranial direct current stimulation (tDCS) while its effects on behavioral and EEG outcomes are assessed. For that, BDs will be randomly assigned to one of three training groups: *combined* (verum cognitive training [CT] and tDCS applied over the right dorsolateral prefrontal cortex [DLPFC]), *cognitive* (CT and sham tDCS), or *control* (sham CT and sham tDCS). Training will occur in three consecutive days, in three sessions. MI will be re-assessed in BDs through a post-training EEG assessment. Alcohol use and craving will be measured at the first EEG assessment, and both 10-days and 3-months post-training. In addition, behavioral and EEG data will be collected during the performance of an alcohol cue reactivity (ACR) task, which evaluates attentional bias towards alcoholic stimuli, before and after the MI training sessions.

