## Statistical Analysis

The first step of the statistical analyses will be to examine the behavioral and EEG correlates of MI among college BDs and non/low-drinkers. For that purpose, the outcomes of the TNTA task collected during the pre-training assessment (T2) in BDs and non/low-drinkers will be compared and correlated with alcohol consumption (AUDIT) and alcohol craving measures (i.e., the PACS' and ACQ-SF-R's scores, and the ERPs and valence/arousal ratings recorded during the ACR task). Secondly, with the purpose of verifying the impact of the *combined, cognitive* and *control* training procedures applied to BDs on psychological, behavioral and neurofunctional measures, the pre-training data (T2) from the 45 BDs will be compared with the post-training data (T4) from the same subjects. Thirdly, to examine potential differences in the psychological, behavioral and neurofunctional effects of the training sessions both in terms of MI abilities and alcohol craving/consumption, the results of the post-training assessment (T4) of the three training groups will be compared.

With regard to the behavioral data, items learned during the learning phase and correctly recalled during the memory test phase will be considered correct responses. Accordingly, the percentage of correct responses (for Think, No-Think and Baseline items) will be computed according to the following formula:

$$\left( \frac{\text{number of correctly recalled items}}{\text{number of previously learned items}} \right) \times 100$$

A mixed-model analysis of variance (ANOVA) with one between-subject factor, Group (non/low-drinkers, BDs), and two within-subject factors, Condition (Think, NoThink, Baseline) and Content (Alcohol, Non-Alcohol) will be conducted on the recall accuracy rate to examine the participants' MI ability at T2. Afterwards, a repeated-measures ANOVA with three within-factors: Moment (T2 and T4), Condition (Think, NoThink, Baseline) and Content (Alcohol, Non-Alcohol) will be performed to explore the training effects on the MI ability of BDs only.

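### The recall ANOVAs meant to examine memory inhibition pre-specify no No-Think versus Baseline contrast, so a difference in Think recall alone could be read as an inhibition effect

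*SAP*

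**What the plan says.** The SAP's Abstract defines the construct: "Memory inhibition (MI), the ability to voluntarily suppress unwanted thoughts or memories". In the task, that corresponds to the No-Think instruction. The protocol's TNT Phase section supplies a reference for it: "The remaining 12 neutral images not depicted in this phase will serve as a baseline condition". Research question 2 in the protocol, on training, is also specific to No-Think: "Specifically, will the BDs show a reduced recollection of no-think images", with the emphasis on alcoholic images.

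The SAP's Statistical Analysis section computes percent recall separately for Think, No-Think and Baseline items. It then describes the T2 analysis as a mixed ANOVA with Group between subjects and "two within-subject factors, Condition (Think, NoThink, Baseline) and Content (Alcohol, Non-Alcohol) will be conducted on the recall accuracy rate", in order to examine "MI ability at T2". A second ANOVA has three within-subject factors: Moment, the same three-level Condition, and Content. It "will be performed to explore the training effects on the MI ability of BDs only".

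For neither analysis does the section say which main effect or interaction is the MI test, or name a contrast, a follow-up comparison or a rule of interpretation. The second ANOVA has no training-arm factor. The section does announce a comparison of the three arms at T4, but gives no model for recall in that step.

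**The concern.** Inhibition shows as No-Think recall falling below Baseline recall. A three-level Condition interaction has 2 degrees of freedom and responds to any pattern among the three means. One such pattern is a shift in Think with No-Think and Baseline unchanged.

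The design makes that pattern plausible after training. According to the protocol's section on the task variations, active training keeps the structure of the original task, so Think trials are practised. False training replaces the whole TNT phase with a categorization task. Trained participants could therefore improve at cued retrieval without any change in suppression.

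At stake is the main behavioral conclusion, both for binge drinkers against non/low-drinkers and for training. If the comparison that carries the conclusion is chosen after the data are seen, a significant interaction is weak evidence about inhibition. The SAP also plans to correlate the behavioral correlates of MI with AUDIT, ACQ-SF-R and PACS scores. That needs one MI score per person, and the recall analysis defines none.

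**Working it through.** The plan gives no effect size, SD, correlation or alpha for recall, so there is no figure of its own to reproduce. The check asks how the planned interaction behaves when only Think differs.

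**Inputs from the documents.** 45 binge drinkers and 45 non/low-drinkers; 12 Think, 12 No-Think and 12 Baseline items; 18 alcohol and 18 non-alcohol pictures.

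**Assumptions.** Alpha 0.05; sphericity; recall averaged over Content; within-person correlation ρ = 0.5, varied from 0.3 to 0.7; Think-only differences d of 0.3, 0.5 and 0.7 SD.

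**Group x Condition.** Centring the group differences (d, 0, 0) gives (2/3, −1/3, −1/3)d, whose sum of squares is (2/3)d². The residual variance is 1 − ρ in SD units. The noncentrality is therefore

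λ = (n/2) × d² × (2/3) / (1 − ρ), with 2 and 2(2n − 2) = 176 df.

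For n = 45 and ρ = 0.5, λ = 22.5 × (2/3) / 0.5 × d² = 30d².

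| Think-only difference | λ | Significant, formula | Significant, simulation | No-Think minus Baseline contrast |
|---|---|---|---|---|
| 0.3 SD | 2.7 | 29% | 28% | 5% |
| 0.5 SD | 7.5 | 68% | 68% | 5% |
| 0.7 SD | 14.7 | 94% | 93% | 5% |

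The contrast stays at 5% because its expected value does not involve Think.

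**Sensitivity to ρ.** At 0.3 SD, λ = 1.93 for ρ = 0.3 and 4.5 for ρ = 0.7. The simulated range is 23% to 46%, and the formula agrees within about a point.

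**Moment x Condition.** For the 45 binge drinkers the noncentrality is the same, with 2 and 88 df. The results are about 28%, 67% and 93%.

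**Second model.** This used 12 binomial items per condition, with assumed recall of 80% Think, 75% No-Think and 80% Baseline and a between-subject SD of 10 points. Think-only differences of 5, 10 and 15 points make Group x Condition significant in 28.0%, 82.3% and 99.0% of trials. The contrast gives 4.7%, 5.3% and 5.0%.

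**Power when only No-Think differs.** At 0.5 SD and ρ = 0.5, the omnibus interaction has 68% power and the contrast 65%. For a 10-point difference with a residual SD of 12 points, the figures are 82.5% and 79.8%. The loss is about 2 to 4 points.

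**Alcohol items only.** If balanced, 18 / 3 = 6 alcohol items fall in each condition. That is an upper limit, because the SAP's denominator counts only learned items. In the binomial model with a 10-point No-Think difference, power of the contrast falls from about 77% with 12 items to about 47% with 6, some 30 points. Repeat runs differ by 2 to 3 points.

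**Between arms.** With equal allocation there are 45 / 3 = 15 per arm. For a 10-point difference in change between two arms, power is about 20% to 22% with 12 items and about 12% with 6.

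**The case against.** The strongest reply is that the documents already point to the right cell. MI is defined as suppression, Baseline items are set aside, research question 2 concerns No-Think images, and recall is computed separately by condition. An analyst who follows these would look at the No-Think means before claiming inhibition.

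Much of this stands. A reader might infer that the sponsor will report a Think-driven interaction as inhibition. The documents do not support that: they name no term as the MI test, give no rule that equates a significant interaction with inhibition, and do not rule out follow-up comparisons. A reader might also infer that Think should not be in the model. That does not follow either, since Think is a useful check on retrieval.

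It is also fair that the percentages depend on an assumed correlation and omit Content. They are conditional on a Think-only difference that the documents do not predict.

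The reply does not close the gap. Research question 2 does not name Baseline as the comparator, and a follow-up that is not written down leaves the choice of comparison open until the data are known.

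**Conclusion.** The point holds as a missing pre-specified contrast; the ANOVA itself is not wrong. The planned interactions do not isolate inhibition, and a Think-only difference could make them significant and be read as an inhibition effect. The 28%, 68% and 93% are illustrations under the stated assumptions and should not be quoted as error rates of this trial. That the interaction responds to Think, and the contrast does not, does not depend on the assumptions; the percentages do. The gap affects both the T2 group comparison and the training analysis, and should be closed before the data are analysed.

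**What to change.** In the recall paragraph of the SAP's Statistical Analysis section:

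- Define the MI score per person as Baseline minus No-Think percent recall, for each Content level.
- Make two analyses the main behavioral tests: the Group difference in this score at T2, and the T2 to T4 change in the score compared among the three training arms.
- Keep Content (Alcohol, Non-Alcohol) as a modifier, so that the alcohol-specific effect is estimated with its interval without discarding the other items.
- Report Think recall as a secondary check and the three-level omnibus ANOVAs as secondary.
- Use the same score in the planned correlations.

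No new data are needed. The cost is about 2 to 4 points of power against the omnibus interaction when only No-Think differs and all items are used. Restricting the score to alcohol items could cost about 30 points if the effect is present in both contents. Conversely, if the effect is confined to alcohol items, averaging over Content halves it, which is why the alcohol-specific estimate should be reported alongside. The between-arm comparison, at about 15 per arm, will be imprecise, and the SAP should say so.

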Furthermore, in order to examine the emotional response of participants to alcoholic cues (self-assessed during the ACR task using the Manikin test) at T2, two ANOVAs with Group (non/low-drinkers, BDs) as between-subject factor and with Content (Alcoholic, Non-Alcoholic) as within-subject factor will be conducted for valence and arousal ratings, separately. In addition, to evaluate possible variations in valence and arousal responses as a function of training sessions, new ANOVAs will be performed for each training group with two within-factors - Moment (T2 and T4) and Content (Alcoholic, Non-Alcoholic).

For the TNTA task, we will analyse the ERPs, specifically the mean amplitudes of N2, LPP and frontal slow wave (FSW). A mixed-model ANOVA with one between-subject factor Group (non/low-drinkers, BDs) and four within-subject factors: Condition (Think, NoThink), Content (Alcohol, Non-Alcohol), Region (Left, Midline, Right) and Electrode (2 electrodes) will be conducted on the mean amplitude of each component to explore the MI neural mechanisms during pre-training (T2). A repeated-measures ANOVA with five within-subject factors: Moment (T2 and T4), Condition (Think, NoThink), Content (Alcohol, Non-Alcohol), Region (Left, Midline, Right) and Electrode (two electrodes) will be conducted on the mean amplitude of each component separately, to explore the effects of MI training on the neural activity.

For the ACR task at T2, the mean amplitude of the P1, N1 and P2 ERP components will be analysed by means of separate mixed-model ANOVAs with one between-subject factor Group (non/low-drinkers, BDs) and three within-subject factors: Content (Alcoholic, Non-Alcoholic), Region (Left, Midline, Right) and Electrode (two electrodes of interest). Furthermore, in order to investigate potential MI training effects on the electrophysiological reactivity to alcoholic cues, the amplitude of the abovementioned components will be analysed through repeated-measures ANOVAs using within-subject factors: Moment (T2 and T4), Content (Alcoholic, Non-Alcoholic),

Region (Left, Midline, Right) and Electrode (two electrodes). The behavioral and ERP correlates of MI and alcohol craving/reactivity will be correlated with the scores obtained from AUDIT, ACQ-SF-R and PACS.

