In addition, analysis of the brain FC will also be conducted. FC will be calculated in the four classical bands –i.e., theta (4 – 8 Hz), alpha (8 – 12 Hz), beta (12 – 30 Hz), and low gamma (30 – 45 Hz)- using the Phase Locking Value (PLV) [70]. In a first step, PLV will be calculated separately for each pair of source positions, generating a 1489 x 1489 FC matrix. Secondly, we will average the PLV values of all the links connecting each pair of 58 cortical regions of interest (ROI) according to the Harvard-Oxford atlas, obtaining a 58 x 58 whole-brain FC matrix. For the whole-brain analysis, the PLV value between each pair of ROIs will be compared between groups by an ANCOVA test using Beamformer filter correlation (in order to correct potential source leakage differences between groups) as covariate and gender as factor. The resulting *p*-values will be corrected for multiple comparisons (number of pair comparisons and number of frequency bands) with a False Discovery Rate (FDR) of 0.1. Only links that survived the FDR-corrected threshold will be reported as significant. Once the significant links for each condition have been determined, the FC values will be correlated with the scores obtained from AUDIT, ACQ-SF-R and PACS.

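### No T2-T4 ANOVA written for training effects on recall, ERPs or ratings has a between-arm term, and the three-arm T4 comparison planned for these outcomes has no model

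*SAP*

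**What the plan says.** The SAP's Statistical Analysis section sets out three steps. The first compares binge drinkers (BDs) with non/low-drinkers at T2. In the second, "the pre-training data (T2) from the 45 BDs will be compared with the post-training data (T4) from the same subjects". In the third, "the results of the post-training assessment (T4) of the three training groups will be compared".

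The T2-T4 models that follow are:

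- **Recall:** "a repeated-measures ANOVA with three within-factors: Moment (T2 and T4), Condition (Think, NoThink, Baseline) and Content (Alcohol, Non-Alcohol) will be performed", with the purpose "to explore the training effects on the MI ability of BDs only".
- **TNTA ERPs:** "A repeated-measures ANOVA with five within-subject factors: Moment (T2 and T4), Condition (Think, NoThink), Content (Alcohol, Non-Alcohol"), plus Region and Electrode.
- **ACR ERPs:** "repeated-measures ANOVAs using within-subject factors: Moment (T2 and T4), Content (Alcoholic, Non-Alcoholic"), again plus Region and Electrode.
- **Valence and arousal:** "new ANOVAs will be performed for each training group with two within-factors", namely Moment and Content.

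For functional connectivity (FC), "the PLV value between each pair of ROIs will be compared between groups by an ANCOVA test". Neither the groups nor the time point is named.

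**The concern.** The randomised contrast is between the three training arms, one of which receives sham cognitive training and sham tDCS (Protocol, Quality assurance and randomization). Research questions 2 and 3 in that section ask what memory inhibition training does to recall, to its electrophysiological correlates and to cue reactivity. The SAP abstract expects better suppression after both the combined and the cognitive training. These are questions about differences between arms.

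Both tasks are repeated at T4 under the T2 procedure (Protocol, T4: Post-training EEG Assessment), so some change without training is possible. The sham arm exists to take account of it. A model without a between-arm term cannot use the sham arm in that way, and it cannot separate combined from cognitive training.

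**Working it through.** **Step 1: factors in each model.** Wherever the recall, ERP and rating ANOVAs define a between-subject Group factor, its levels are non/low-drinkers and BDs, and it is used at T2 only. The T2-T4 models for recall and both sets of ERPs list within-subject factors alone. Read literally, they pool all 45 BDs, controls included; they could also be meant arm by arm. For ratings, arm splits the data but is not a factor. On either reading no term compares arms, and no model is attached to step three for these outcomes.

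**Step 2: which change matters.** Practice that is the same in every condition cancels in Moment x Condition, and practice that is the same for both contents cancels in Moment x Content. This holds for recall, ERPs and ratings alike. The problem is change shared across arms in the term actually tested. The SAP does not say which term carries the training claim; a Moment main effect would not have this protection.

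**Step 3: illustration.** The SAP gives no power, effect size, SD or ANOVA alpha, so there is no planned figure to reproduce. The total of 45 BDs comes from the documents. Assumed: 15 per arm (45/3), two-sided alpha 0.05, no training effect, and a shared change of δ SD of the change score in the tested term.

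*Pooled reading.* Paired t-test, 44 df, non-centrality δ√45. At δ = 0.3 this is 0.3 × 6.708 = 2.01.

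| δ | 0 | 0.1 | 0.2 | 0.3 | 0.5 |
|---|---|---|---|---|---|
| P(significant) | 5% | 10% | 26% | 50% | 91% |

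If training does work equally in both active arms (change d) and controls do not change, the pooled estimate is (d + d + 0)/3 = 0.67d.

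*Arm-by-arm reading.* With p the power of a paired t-test at n = 15, the chance that at least one active arm is significant and control is not equals (1 − p)[1 − (1 − p)²].

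| δ | 0 | 0.3 | 0.5 | 0.7 |
|---|---|---|---|---|
| p | 0.050 | 0.192 | 0.438 | 0.713 |
| P(pattern) | 9% | 28% | 38% | 26% |

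The 9% at zero shared change comes from multiple testing alone.

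*Between-arm test.* In simulation with shared change, Group x Moment, T4-only and ANCOVA all reject in about 5% of trials.

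**Step 4: power of the candidate between-arm tests.** Effects (d, d, 0) in single-measurement SD, with ρ the T2-T4 correlation (not given, so a range is shown). The non-centrality of the F test is 15 × (2/3)d²/σ² = 10d²/σ². Here σ² = 1 − ρ² for ANCOVA (df 2, 41), 1 for T4-only and 2(1 − ρ) for Group x Moment (both df 2, 42). Example: d = 0.8, ρ = 0.5, ANCOVA: 10 × 0.64/0.75 = 8.53, power 71%.

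| Power at d = 0.5/0.8/1.0 | ρ = 0.3 | ρ = 0.5 | ρ = 0.7 |
|---|---|---|---|
| ANCOVA | 28/62/82% | 33/71/89% | 46/87/98% |
| T4-only | 26/58/79% | 26/58/79% | 26/58/79% |
| Group x Moment | 19/44/63% | 26/58/79% | 40/81/95% |

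Simulated ANCOVA power agrees to within about 2 percentage points.

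**The case against.** The strongest reply is that the between-arm comparison is already planned. Step three commits to comparing the three training groups at T4 on psychological, behavioral and neurofunctional effects, and under randomisation that comparison is valid. Nothing says that the T2-T4 ANOVAs replace it, and the recall and TNTA ERP models are described as exploratory. This stands. A reader might infer that the plan has no between-arm test at all; the documents do not support that. What is missing is the model: outcome contrast, use of the T2 value, and arm contrasts. Meanwhile, the models that are spelled out and tied to training effects cannot isolate training.

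A reader might also take 50% or 91% as the trial's expected false-positive rate. That is not supported either. The documents give no size for shared change, a change of 0.1 SD gives only about 10%, and uniform practice cancels in the interactions. The arm-by-arm pattern is an informal way of reading three separate tests; the SAP states no such decision rule.

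The FC ANCOVA might cover the training arms. Because its groups and time point are unnamed, this can be neither assumed nor ruled out, and it would not supply a model for the other outcomes.

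**Conclusion.** The point holds and should be fixed. It is structural: for recall, TNTA ERPs, ACR ERPs, valence and arousal, no model in the SAP text compares the randomised arms, although the comparison is announced. That conclusion needs no assumed numbers. The error rates and power figures are illustrative and rest on 15 per arm, alpha 0.05, and assumed values of δ, d and ρ. Confidence in the structural finding is high.

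**What to change.** Make step three the test of training. For each outcome, fit an ANCOVA of the T4 contrast on the same contrast at T2, with Training Group (combined, cognitive, control) as the between-subject factor. Follow it with combined vs control and cognitive vs control under a stated multiplicity adjustment. If a claim about what tDCS adds is intended, put combined vs cognitive in the same family. Contrasts:

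- **Recall:** Baseline minus NoThink, alcohol items.
- **TNTA ERPs:** NoThink minus Think, alcohol items, averaged over the Region and Electrode sites of each component or over a prespecified subset.
- **ACR ERPs, valence and arousal:** Alcoholic minus Non-Alcoholic, with ERPs averaged over sites in the same way.

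State which groups and time point the FC ANCOVA covers. Keep pooled or within-arm Moment effects, labelled descriptive. Adding Training Group and its Moment interaction to the existing models would also cure the defect, but ANCOVA has higher power at each ρ examined.

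The cost is SAP wording only; T2 and T4 data are already collected under the plan. The downside is modest power: at d = 0.5 the ANCOVA reaches only 28% to 46% over the ρ range shown, and the SAP should acknowledge this.

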**Discussion:** This protocol will provide the first behavioral and neurofunctional assessment of MI in BD. Along with poor MI abilities, BDs are expected to show alterations in the amplitude of several event-related potentials (ERPs) linked to MI (e.g., N2 and late parietal positivity) as well as abnormal functional connectivity (FC) patterns within/between regions associated with MI (e.g., DLPFC and hippocampal/parahippocampal regions). Results should also demonstrate the effectiveness of the training protocol, with BDs exhibiting an improved capacity to suppress alcohol-related memories after both *combined* and *cognitive* MI training, along with a significant reduction in alcohol use and craving in the short/medium-term. Furthermore, this protocol should also lead to significant modifications in the ERP and FC patterns, reflecting stronger MI capabilities and reduced alcohol cue reactivity in trained BD participants. Finally, in case the protocol provides significant results, these findings might have major implications for the understanding and treatment of alcohol misuse.

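### The recall, rating and ERP ANOVAs name no hypothesis term, alpha or multiplicity rule, so at a 0.05 level a chance training effect among their 88 Moment terms is very likely

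*SAP*

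**What the plan says.** The SAP's Statistical Analysis section sets out four kinds of outcome, each analysed at T2 and again for T2 against T4.

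- **TNTA recall.** At T2, an ANOVA with "one between-subject factor, Group (non/low-drinkers, BDs), and two within-subject factors, Condition (Think, NoThink, Baseline) and Content (Alcohol, Non-Alcohol"). For training, "a repeated-measures ANOVA with three within-factors: Moment (T2 and T4), Condition (Think, NoThink, Baseline) and Content (Alcohol, Non-Alcohol"), in binge drinkers only.
- **ACR valence and arousal ratings.** At T2, "two ANOVAs with Group (non/low-drinkers, BDs) as between-subject factor and with Content (Alcoholic, Non-Alcoholic) as within-subject factor". For training, "new ANOVAs will be performed for each training group with two within-factors - Moment (T2 and T4) and Content (Alcoholic, Non-Alcoholic").
- **TNTA ERPs (N2, LPP, FSW).** Five factors at T2 (Group, Condition, Content, Region, Electrode) and five for training (Moment in place of Group). The training model "will be conducted on the mean amplitude of each component separately, to explore the effects of MI training on the neural activity".
- **ACR ERPs (P1, N1, P2).** Four factors at T2 and four for training.

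No alpha is given for these ANOVAs, no main effect or interaction is singled out, and no adjustment is described. The one correction in the section is for functional connectivity, where p-values are "corrected for multiple comparisons (number of pair comparisons and number of frequency bands) with a False Discovery Rate (FDR) of 0.1" and "Only links that survived the FDR-corrected threshold will be reported as significant".

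The SAP's Abstract, under Discussion, says: "Results should also demonstrate the effectiveness of the training protocol".

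**The concern.** A full-factorial ANOVA with five factors returns 31 F tests. Research question 3 in the protocol (Quality assurance and randomization) asks only whether the electrophysiological correlates change with training. Any term containing Moment could be offered as a yes, including interactions with Region or Electrode that nobody predicted. In the same way, any term containing Group at T2 could be offered as a binge-drinking effect. Nothing written in advance tells the analyst or the reader which term counts, so a few chance interactions could be reported as evidence that training altered neural activity. The authors control multiplicity for connectivity but leave it open for everything else.

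**Working it through.** **Plan's own figure.** There is none to reproduce: no alpha, number of tests or error rate is stated for the ANOVAs.

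**Count.** A full-factorial ANOVA with k factors tests 2^k − 1 effects, of which 2^(k−1) contain any given factor. Factors and numbers of ANOVAs are those in the SAP's Statistical Analysis section. Recall and ERP training models are taken as pooled over the 45 binge drinkers, as written; rating models are run in each of three training groups.

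| ANOVAs | Number | k | Effects | With Group or Moment |
|---|---|---|---|---|
| Recall, T2 | 1 | 3 | 1 × 7 = 7 | 4 Group |
| Recall, T2–T4 | 1 | 3 | 1 × 7 = 7 | 4 Moment |
| Ratings, T2 | 2 | 2 | 2 × 3 = 6 | 4 Group |
| Ratings, T2–T4 | 3 × 2 = 6 | 2 | 6 × 3 = 18 | 12 Moment |
| TNTA ERPs, T2 | 3 | 5 | 3 × 31 = 93 | 48 Group |
| TNTA ERPs, T2–T4 | 3 | 5 | 3 × 31 = 93 | 48 Moment |
| ACR ERPs, T2 | 3 | 4 | 3 × 15 = 45 | 24 Group |
| ACR ERPs, T2–T4 | 3 | 4 | 3 × 15 = 45 | 24 Moment |

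- Total: 7 + 7 + 6 + 18 + 93 + 93 + 45 + 45 = 314.
- Moment terms: 4 + 12 + 48 + 24 = 88.
- Group terms: 4 + 4 + 48 + 24 = 80.
- Neither: 314 − 88 − 80 = 146.

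**Error rates.** With m tests at level α and all nulls true, the expected number of false positives is m × α. Under independence the chance of at least one is 1 − (1 − α)^m. Alpha is an assumption, so two levels are shown.

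| Terms | m | Expected, α = 0.05 | At least one, α = 0.05 | Expected, α = 0.01 | At least one, α = 0.01 |
|---|---|---|---|---|---|
| All Moment | 88 | 4.4 | 0.99 | 0.88 | 0.59 |
| All Group | 80 | 4.0 | 0.98 | 0.80 | 0.55 |
| ERP Moment | 72 | 3.6 | 0.98 | 0.72 | 0.52 |
| Moment, one TNTA ERP ANOVA | 16 | 0.8 | 0.56 | 0.16 | 0.15 |

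**Dependence.** The tests share subjects, so independence is too simple. A simulation covered the 76 Moment terms in the pooled recall and ERP models (4 + 48 + 24), with n = 45, α = 0.05, 1,000 runs and assumed correlations.

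| Correlation across components | Correlation among effects | At least one false positive |
|---|---|---|
| 0 | 0 | 0.98 |
| 0.5 | 0 | 0.96 |
| 0.8 | 0 | 0.94 |
| 0.5 | 0.3 | 0.94 |
| 0.8 | 0.3 | 0.90 |
| 0.8 | 0.5 | 0.80 |
| 0.8 | 0.8 | 0.62 |

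The mean number of false positives stayed between 3.7 and 4.8, against a nominal 76 × 0.05 = 3.8. Correlation makes false positives cluster but does not reduce their average number.

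**Sensitivity of the count.** If the recall and ERP training models were also run in each of the three groups, the total would be 314 + 2 × (7 + 93 + 45) = 604, with 88 + 2 × 76 = 240 Moment terms. Correlations with AUDIT, ACQ-SF-R and PACS, and the announced three-group comparison at T4, come on top of the 314.

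**The case against.** The strongest reply is that these are secondary, exploratory analyses. The SAP uses the word explore for the ERP models, and the protocol (T5: Monitoring of alcohol consumption and alcohol craving) calls craving and consumption primary. Components, regions and numbers of electrodes are fixed in advance. This limits the weight of the point, but it does not answer it: no rule says that ERP findings will be reported as exploratory, and the Abstract expects significant ERP changes as a sign of better memory inhibition.

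Several stronger readings are tempting, and the documents do not support them.

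- *That 314 tests at 0.05 imply 15.7 chance findings.* The 0.05 is not in the text available, and the start of the SAP is missing from that text, so a level stated there cannot be excluded. The 146 terms without Group or Moment are task or scalp-topography effects. They cannot be read as training or drinking effects, and many may be truly non-null.
- *That no hypothesis is stated at all.* Research question 2 in the protocol predicts lower recall of no-think images after training, mainly alcoholic ones. In effect this points to Moment × Condition × Content. The Abstract also names N2 and late parietal positivity for the group difference. What is missing is the link from hypothesis to ANOVA term, and for the ERP training models even the wording is general.
- *That correcting only connectivity contradicts the rest of the plan.* Connectivity is a mass search: 58 × 57 / 2 = 1,653 pairs × 4 bands = 6,612 tests. Six pre-chosen components are a different setting. Leaving them unadjusted is a gap and not an inconsistency.
- *That effectiveness will be claimed from the ERPs.* The effectiveness sentence in the Abstract goes on to memory suppression, alcohol use and craving; ERP and connectivity changes follow in a separate sentence.

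**Conclusion.** The concern holds in a limited form. No ANOVA term is designated as the hypothesis test, and no alpha or multiplicity rule is given outside connectivity. At an assumed 0.05 with all nulls true, about 4.4 of the 88 Moment terms would be significant by chance, and at least one is very likely. Near certainty (0.99) requires independence as well as the 0.05 level. Strong correlation, or an alpha of 0.01, brings the chance down to about 0.6. The point concerns how ERP, recall and rating results may be interpreted. It does not touch the outcomes called primary, and it is worth settling before the data are analysed.

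**What to change.** State alpha for the ANOVAs and name one confirmatory term per outcome.

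- **T2:** Group × Condition × Content for TNTA recall and ERPs; Group × Content for ACR ERPs and ratings.
- **Training:** add Training group as a between-subject factor to the T2–T4 ANOVAs. Use Training group × Moment × Condition × Content for TNTA and Training group × Moment × Content for ACR. The recall and ERP training models lack this factor at present, so they cannot address the randomised comparison.
- **Multiplicity:** apply Holm across the three ERP components of each task. For the ERPs this gives four families of three, or 12 confirmatory tests. They replace 48 + 24 + 48 + 24 = 144 Group or Moment terms, which carry 144 × 0.05 = 7.2 expected false positives at the assumed level.
- **Everything else:** report as exploratory with FDR control, a method the SAP already uses.

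No new data are needed. The cost is more than wording, because the training models must be respecified. Some Region or Electrode interactions will no longer be called significant. With 45 binge drinkers in three groups (15 each if split equally), the interaction tests will have limited power, and the SAP should say so.
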